This section has been renamed “CTSU Registration Procedures” and renumbered as [Section 6.2](#). It has been updated with the current CTSU boilerplate language. All subsequent sections have been renumbered.

Section 6.3.3 Submitting Regulatory Documents (page 25):

This section has been renumbered as [Section 6.2.3](#). The suite number in the CTSU mailing address has been changed to “3000.”

Section 10.0 Adverse Event (AE) Reporting and Monitoring (page 40):

All references to “AdEERS” have been replaced with “CTEP-AERS” due to the new CTEP expedited reporting requirements.

Section 10.1 Adverse Event Characteristics (page 40):

- After the first sentence, a second sentence has been added due to the change in CTCAE version for reporting serious adverse events.
- The “4.0” in the third sentence has been changed to “5.0” with regards to the new CTCAE version number used for expedited adverse event reporting.
- The last four sentences have been added to describe the use of CTEP-AERS.

Section 10.11 Adverse Event Monitoring, Data Collection and Reporting (page 40):

- In the fourth sentence of the second paragraph, AdEERS has been replaced with the CTEP-AERS for expedited adverse event reports.
- In the fifth sentence, the phrase “using CTCAE version 5.0” has been added due to the change in CTCAE version requirements for expedited reporting.

Section 10.33 Death (page 42):

- The first four bullets have been deleted.
- The now first bullet point has been replaced with updated CTCAE version 5.0 language.
- Three more bullet points have been added to the end of the section to reflect updated reporting requirements for pregnancy loss and neonatal death in CTCAE version 5.0.

Section 10.34 Secondary Malignancy (page 43):

This section has been replaced in its entirety with the updated CTEP-AERS reporting requirements.

Section 10.4 Expedited Reporting Requirements: Studies Using Commercial Agent(s) ONLY (page 44):

- The sentence beginning with “Refer to 10.41...” under the chart has been removed due to the removal of the 10.41 contact table.
- The sentence beginning with “in the rare event...” has been replaced with a new sentence with updated CTEP contact information.

Section 10.41 (Contact Information for NCI Safety Reporting):

This section has been removed as safety reporting is now done through CTEP-AERS (website URL listed

previously).

Section 16.64 Adverse Events (page 59):

1.0 Background

1.1 Introduction

Over 207,090 women are diagnosed with invasive breast cancer in the United States each year (Jemal *et al.*, 2010). An additional 52,000 are diagnosed with ductal carcinoma in situ (DCIS) (American Cancer Society statistics). Of women newly diagnosed with breast cancer, studies have reported that between 14 and 51 percent will undergo preoperative MRI (Arrington *et al.*, 2009; Jones *et al.*, 2009; Sorbero *et al.*, 2009; Wood, 2009). In an era of increasing breast MRI usage and improved radiographic imaging modalities, the incidence of preoperatively identified multiple ipsilateral primary breast cancers (MIBC) including multicentric (MC) and/or multifocal (MF) breast cancer is increasing (Bendifallah *et al.*, 2010; Berg and Gilbreath, 2000; Berg *et al.*, 2011; Houssami *et al.*, 2008; Moon *et al.*, 2002; Wilkinson *et al.*, 2005). Data show that MRI is more accurate than mammography alone in detection of MIBC. A meta-analysis performed in 2008 demonstrated that MRI identified additional tumor foci in 16 % of newly diagnosed breast cancer patients (Houssami *et al.*, 2008). Increased utilization of bilateral whole breast sonography in women with a new breast cancer diagnosis has also led to increasing detection of MIBC (Wilkinson *et al.*, 2005). Other novel imaging modalities, for example positive emission mammography (PEM), breast specific gamma imaging (BSGI) and Molecular Breast Imaging (MBI), may continue to increase the detection of MIBC. A PEM/MRI study reported 14 % of patients enrolled were converted to mastectomy based on findings from these novel images (Berg and Gilbreath, 2000).

The prevalence of MIBC ranges across studies from 13 to 75 % but the true incidence is difficult to ascertain given the varying definitions of multifocal and multicentric used between studies (Bendifallah *et al.*, 2010). Classically, multifocal disease is defined as two or more foci of disease within the same quadrant of the breast and multicentric disease as two or more foci of disease in different quadrants of the breast. Differentiating between multifocal and multicentric tumors by the use of quadrants of the breast is not related to tumor biology and is somewhat arbitrary. A tumor at 11 o'clock can be 2 cm away from a tumor at the 1 o'clock position and these would be classified as multicentric, whereas 2 tumors both at the 2 o'clock position that are 5 cm apart may be classified as multifocal. This issue is more pronounced closer to the nipple, where the distance between quadrants is smaller than in the periphery of the breast. The true biologic question is whether women with more than one focus of breast cancer can undergo breast conservation with minimal morbidity and whether local recurrence is equivalent to women with unifocal disease. Therefore, for this study we use the term MIBC defined as two or more foci of biopsy proven breast cancer separated by at least 2 cm of normal breast tissue.

Studies have confirmed that the rate of mastectomy is increasing in the United States (Katipamula *et al.*, 2009; McGuire *et al.*, 2009). This may be linked to several factors including use of pre-operative MRI and of the resulting increase in detection of MIBC (Bedrosian *et al.*, 2003; Bleicher *et al.*, 2009; Fischer *et al.*, 1999; Lee *et al.*, 2004; Morrow and Harris, 209; Touttle *et al.*, 2007). Based on historic, retrospective studies from the late 1980s and early 1990s (Kurtz *et al.*, 1990; Leopold *et al.*, 1989; Wilson *et al.*, 1993), most surgeons are reluctant to proceed with breast conservation therapy (BCT) for women with multicentric or multifocal breast cancer due to a perceived high risk of local recurrence (LR). However, no scientific evidence exists to support this increased mastectomy rate in MIBC patients (Fisher, 2011). The emotional impact of mastectomy on body image and quality of life is well documented (Fung *et al.*, 2001; Kiebert *et al.*,

1991); Zhao *et al.*, 2003). The emotional benefit of breast conservation has driven surgeons in the United States and Europe to recommend breast conservation to over 50 % of women with a single, early stage malignant focus for three decades (Hershman *et al.*, 2009; Komenaka *et al.*, 2010). BCT is associated with improved patient satisfaction and quality of life and has been shown to be cost effective (Al-Ghazal *et al.*, 2000; Barlow *et al.*, 2001; Norum *et al.*, 1997)

Retrospective studies from the 1980s and early 1990s demonstrated an increased risk of local regional recurrence in women with two or more synchronous lesions in the breast in comparison to women with unifocal cancers treated with breast conservation. However, imaging was less advanced and the margins in the older trial were assessed grossly rather than microscopically (Cho *et al.*, 2002; Kaplan *et al.*, 2003; Kurtz *et al.*, 1990; Leopold *et al.*, 1989; Wilson *et al.*, 1993)

In contrast, none of the retrospective studies published since 1993 have reported a significant increase in local recurrence rates in women with multicentric/multifocal breast cancer who have been treated with BCT (see Table 1.1) (Cho *et al.*, 2002; Gentilini *et al.*, Hartsell *et al.*, Kaplan *et al.*, 2003; Lim *et al.*, 2009). Multiple, recent retrospective studies support the safety of breast conservation in women with MIBC and confirm a rate of recurrence that is comparable to rates observed in women with unifocal disease (Bauman *et al.*, 2010; Cho *et al.*, 2002; Gentilini *et al.*, 2009; Hartsell *et al.*, 1994). The largest of these contemporary trials, by Gentilini *et al.*, reviewed 476 patients with multicentric (12 %) and multifocal (88 %) invasive breast cancer treated between 1997 and 2002. All patients underwent BCT. Despite significant nodal disease in the study population (55 % of all patients), the local recurrence rate in this trial was 5.1 % at 5 years (Gentilini *et al.*, 2009). In this study, 98.3 % of the patients received adjuvant systemic therapy with 12.6 % receiving adjuvant chemotherapy alone, 40.1 % hormonal therapy alone, and 45.6 % both chemotherapy and endocrine therapy. Adjuvant whole breast radiation was delivered to 95 %. Also of interest, a retrospective study of women with MIBC treated with neoadjuvant chemotherapy has documented 5 year locoregional failure rates of 7 % in patients with MIBC (Oh *et al.*, 2006).

Table 1.1. Recurrence Rates in Multicentric/Multifocal Breast Cancer by Study

Primary Author of Study	Surgical years	Number of Patients (n)	Median Follow-up (months)	Number of Recurrences	Outcome
Leopold	1968–1981	10	64	4	NA
Kurtz	1975-1983	61	71	15	NA
Wilson	Prior to 12/1988	13	71	3	6 year LRR: 25 %
Fowble	1982-1989	57	48	NA	5 year LRR: 8 %
Hartsell	1977-1989	27	53	1	NA
Cho	1989-1997	15	76	0	NA
Kaplan	1989-2002	36	45	1	NA
Gentilini	1977-2002	476	73	24	Cumulative incidence recurrence at 5 years: 5.1 %
Lim	1990-2003	147	59	3	5 year locoregional recurrence rate: 4.7 %

Table adapted from Bauman *et al.*, 2010.

MIBC today includes patients with 2 small foci of disease detected on screening digital mammogram and/or MRI compared to decades ago when MIBC often referred to a palpable mass. Introduction of routine screening mammography and increased patient awareness has led to identification of breast cancer when tumors are smaller in size and early stage breast cancer has better survival compared to more advanced disease.

Therefore, more MIBC patients today are eligible for BCT at time of diagnosis due to the smaller tumor size and disease burden, as compared to the 1980s and 1990s when most women with MIBC presented with larger, palpable tumors. Moreover, in women with newly diagnosed breast cancer who undergo MRI for surgical planning, additional malignant lesions which alter the surgical plan (multicentric/multifocal lesions) are detected in 8 to 27 % of patients. This makes it important for us to reassess the indications for BCT versus mastectomy in women with MIBC in 2012.

The European Breast Cancer Conference (EBCC) has recommended standard preoperative breast MRI in all women with newly diagnosed breast cancer given the significant number of additional multicentric/multifocal cancers identified using this modality (6th European Breast Cancer Conference, Berlin, Germany, 15-19 April 2008). In the United States, the role of preoperative breast MRI remains more controversial and as such it is difficult, therefore, to determine how many centers are utilizing routine preoperative MRI. Using a conservative rough estimate of 30% of breast centers utilizing

routine breast MRI (the average of 14 to 51 % documented in the literature (Arrington *et al.*, 2009; Sorbero *et al.*, 2009) we would expect over 55,000 women with breast cancer to undergo breast MRI for surgical planning. Currently, meta-analysis suggests a 16 % incidence of identification of a second primary in the ipsilateral breast following a cancer diagnosis with further work-up after detection of the initial tumor (Houssami *et al.*, 2008). Given the older retrospective case studies in the literature, the majority of surgeons continue to recommend mastectomy for women with multicentric breast cancer and many with multifocal breast cancer. Based on estimates above, over 17,000 women per year will be triaged to mastectomy based on current algorithms.

1.2 Current Study Rationale

1.2.1 Study Design

While these retrospective data from the modern era described above are encouraging, the safety of BCT in MIBC has not been documented in a prospective fashion. A multicenter study with a uniform and consistent follow-up schedule, defined criteria for recurrence, and strict statistical analysis is necessary to definitively ascertain the safety of breast conservation in the MIBC population. Although an ideal trial design would be a randomized study comparing BCT with mastectomy for women with MIBC, this is felt not to be feasible due to increasing appreciation for shared decision making in the breast cancer population. Discussion with American College of Surgeons Oncology Group (ACOSOG) breast investigators, patient advocates and the Breast Oncology Local Disease (BOLD) taskforce have all indicated that a randomized trial design would not be well supported by patients or physicians. Both patient and surgeon bias would negatively impact timely patient accrual. Therefore, a prospective single arm Phase II trial to address the incidence of local recurrence in women undergoing breast conservation surgery and radiation therapy for MIBC is proposed.

1.2.2 Prognosis

Controversy exists surrounding the prognosis and treatment of MIBC. No prospective trial has addressed this issue. Limited retrospective data debunk the notion that MIBC is an independent risk factor for worsened overall survival (Bendifallah *et al.*, 2010; Pederson *et al.*, 2004). A study by Nos *et al.* reviewed 56 women treated with BCT for MIBC in comparison with 132 women who underwent mastectomy for MIBC. In this retrospective study, no differences in overall survival or local recurrence were detected. Similarly, a study by Oh *et al.* reviewed this question in a population of women with clinically detected MIBC treated with neoadjuvant chemotherapy. This study of 706 women treated with mastectomy, mastectomy and adjuvant radiation or breast conservation for MIBC concluded that MIBC does not predict for inferior outcome (Oh *et al.*, 2006).

1.2.3 Tumor Heterogeneity

This trial may also have timely and important translational science implications. Interest in cancer stem cells and tumor heterogeneity is increasing and a better understanding of these concepts may lead to novel diagnostic, therapeutic and

preventive strategies. As has been described in hematologic malignancies, human breast cancers are heterogeneous, both in their pathology and in their molecular profiles (Hwang-Verslues *et al.*, 2009; Shipitsin *et al.*, 2007) This heterogeneity may be the result of cancer stem cells/progenitor cells which are capable of differentiation along divergent pathways (Nakshatri *et al.*, 2009) Heterogeneity exists both within and between breast cancers. The intrinsic heterogeneity in the MIBC population provides an *in vivo* platform to better understand the variation within individual tumors in a given patient but more importantly, between 2 or more tumors in a given patient. This may expand the growing body of knowledge regarding causation of breast cancer, treatments and prognosis.

In an era of individualized medicine, further understanding of the biology of MIBC is required. We have increased understanding of cancer tumor cells and tumor heterogeneity. For women with more than one tumor, understanding whether these tumors are the same or different is important to guide therapy and the correlative science section of this study (see Section 14.0) will evaluate the similarities and differences of multiple foci of disease within the breast.

1.24 Cosmesis

1.241 4-point Scoring System of Breast Cosmesis (Winchester and Cox, 1992) A single item question will be administered asking both the patient and her surgeon to assess the overall cosmetic result (excellent, good, fair, and poor) (Olivotto *et al.*, 1989; Winchester and Cox, 1992). This questionnaire is also being used in the trial NSABP B-39. Olivotto *et al.* also used this single item questionnaire to assess technical factors impacting whether a patient considered the cosmesis a failure following BCT. In general, patients with a fair or poor score are considered to be a cosmetic “failure”. Olivotto *et al.* demonstrated that cosmetic scores for patients classified as excellent or good cosmetic score remained consistent after 3, 5, and 7 years in 88 %, 90%, and 78 % of the patients, respectively.

1.242 BREAST-Q®

The BREAST-Q®, a patient-reported outcome (PRO) instrument for breast surgery patients, was recently developed to address the lack of instruments to measure outcome in the breast surgical population (Pusic *et al.*, 2009). The questionnaire was developed with strict adherence to guidelines recommended by the Scientific Advisory Committee of the Medical Outcomes Trust and the US Food and Drug Administration (Lohr, 2002; USDHHS, FDA, CDER, CBER and CDRH (2009)). This process included development of a conceptual framework, item generation, scale formation with item reduction, and psychometric evaluation. At present, the BREAST-Q® contains three modules (post mastectomy reconstruction, breast reduction and breast augmentation), each with a preoperative and postoperative version. Each module includes six independent scales (satisfaction with breasts, satisfaction with overall outcome, psychosocial well-being, sexual well-being, physical well-being and satisfaction with care). Psychometric evaluation

suggests that it exceeds criteria for rigorous measurement as established by quality of life researchers and government regulatory bodies internationally. More specifically, each scale fulfilled both Rasch and traditional psychometric criteria (including person separation index 0.76 to 0.95; Cronbach's alpha 0.81 to 0.96; and test-retest reproducibility 0.73 to 0.96). The Breast Q was developed using patient interviews, focus groups, expert panels, and a literature review to develop a conceptual framework and a list of questionnaire items.

Current efforts are now underway to develop a fourth module of the BREAST-Q[©] (the 'Breast-conserving therapy (BCT)' module) to specifically evaluate quality of life in breast cancer patients who undergo BCT. The addition of this new module will allow meaningful comparisons of groups of patients who elect to undergo BCT, mastectomy, or mastectomy with reconstruction. Preliminary versions of the scale have been developed from three sources: review of the literature; qualitative interviews with patients; and expert opinion. Semi-structured, open-ended interviews (n = 30) were recorded, transcribed and analyzed for content. Standard qualitative techniques were then used to identify key domains or themes that emerge. Questionnaire items were developed to reflect these domains and were phrased to reflect terminology and statements typically used by patients. The preliminary measure was then pre-tested in a small sample of patients (n = 20) to clarify ambiguities in the wording of items, and determine acceptability and completion time (personal communication).

Field-testing of this preliminary instrument is now underway (personal communication). Using Rasch analysis, seven measurement criteria will be examined as follows: clinical meaning, thresholds for item response options, item fit statistics, item locations, differential item functioning, correlations between standardized residuals, and person separation index. The aim will be for each scale to consist of a set of clinically meaningful items that satisfy requirements for measurement. This goal will be achieved by choosing a set of items hypothesized to constitute a scale for each area, analyzing the observed data against measurement criteria and making decisions on item selection or deletion. Following item reduction, confirmatory tests on the resultant questionnaire will be performed using traditional psychometric methods in order to enable comparison with existing breast scales and meet regulatory requirements. To this end, five measurement properties will be examined: data quality, tests of scaling assumptions, acceptability, reliability, and responsiveness.

In this study, we will use the independent scales for satisfaction with breasts and satisfaction with overall outcome from the Breast Q[©] BCT module. Although the final version of the BCT module is still being finalized, the individual questions will not change and no questions will be added, therefore using these questions will enable calculation of a score once the Breast Q[©] BCT scoring is complete.

1.243 Breast Lymphedema (BLE) Symptom Survey (Degnim *et al.*, 2008).

Lymphedema in the ipsilateral arm is a well-recognized complication following breast/axillary surgery, but can also occur in the breast after surgery. We have previously evaluated clinical and surgical factors associated with the development of postoperative breast lymphedema (BLE); yet, BLE diagnosis is currently non-standardized and is based on clinical impression.

Previously, we prospectively evaluated patients undergoing non-mastectomy procedures for signs and symptoms of lymphedema in the operated breast. BLE diagnosis was based on a graded physical exam targeting clinical signs of diffuse skin edema, erythema, and their location. Diagnosis was independent of patient reported symptoms. Additionally, patients also rated symptoms in their operated breast for heaviness, discomfort, redness, visible swelling and associated degree of distress using a 10-point scale (“not at all” = 0 to “a lot” = 10). In subjects with clinical BLE, skin edema and breast erythema were observed in 26/26 (100 %) and 13/26 (50 %), respectively, compared to 5/38 (13 %) and 4/38 (11 %) without clinical BLE, respectively. BLE was observed in more than one quadrant for the majority of patients with BLE (skin edema 18/26 = 69 %, and erythema 10/13 = 77 %). Additionally, BLE patients had significantly higher scores for breast heaviness, discomfort, redness, and swelling and distress associated with these symptoms was significantly elevated only for symptoms of breast heaviness (mean 3.4 vs. 1.0, $p = 0.01$) and discomfort (mean 2.9 vs. 1.4, $p = 0.03$).

Patients undergoing lumpectomy for MIBC and breast radiation with boost to both tumor beds are hypothetically at increased risk of BLE. We will evaluate the incidence of BLE and symptoms as diagnosed using clinical examination along with the same questionnaire used in the previous study to see if BLE is more common in women treated with BCT for MIBC than reported in our previous BLE study evaluating patients undergoing lumpectomy and radiation for unifocal breast cancer.

1.25 Linear Analogue Self-Assessment (LASA)

Both fatigue and overall perception of quality of life will be assessed using LASA. Evidence has arisen indicating that baseline single-item assessments of fatigue and overall quality of life are strong prognostic indicators for survival in cancer patients, independent of performance status (Sloan *et al.*, 2009; Tan *et al.*, 2008).

2.0 Goals

2.1 Primary Clinical Goal

To assess the local recurrence (LR) rate with breast conservation in patients with multiple ipsilateral primary breast cancer (MIBC).

2.2 Secondary Clinical Goals

2.21 Conversion Rate to Mastectomy

To examine the conversion rate to mastectomy secondary to persistent positive margins; poor cosmesis within the first year of attempting breast conservation surgery (BCS) or inability to satisfy the radiation dose constraints on the boost to the lumpectomy bed of each site of disease.

2.22 Analysis of Patients Without Negative Margins

To assess whether patients who did not undergo re-excision for close margins (< 2 mm) have a higher local recurrence (LR) rate than patients for whom negative margins were achieved.

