7.2 Surgery

Patients undergoing breast conserving therapy (BCT) for multiple ipsilateral breast cancers should have all lesions resected to negative margins, either using one lumpectomy or two/three separate lumpectomy incisions at the discretion of the surgeon. Lumpectomy specimens must be oriented and submitted for pathological assessment of margins. Intra-operative confirmation of tumor resection is recommended with intra-

operative specimen radiograph. All sites of biopsy proven malignancy (DCIS or invasive breast cancer) and atypia (atypical ductal hyperplasia (ADH), atypical lobular hyperplasia (ALH) and flat epithelial atypia (FEA)) should be resected at time of surgery.

Primary tumor bed will be defined as the area of invasive and/or DCIS and include nearby small satellite nodules within 1 centimeter of the index lesion.

Each tumor must be resected to negative margins (no tumor at ink).

Re-excision should be done to achieve negative margins as needed. Patients with persistent positive margins should be converted to mastectomy or go off study. For patients who convert to mastectomy within one year of initial surgery, see Section 13.2.

Where possible, surgical clips must be placed to outline the surgical bed for all patients. For patients where an oncoplastic approach to the surgical resection is undertaken, clips must be placed to outline the surgical bed. For the oncoplastic patients, the tissue rearrangement must be clearly documented in the operative report to facilitate radiation planning. Oncoplastic tissue rearrangement by the breast surgeon or plastic surgeon is permitted. Planned autologous tissue flaps (such as latissimus flap, etc.) or implants are not permitted.

Axillary staging is required for all invasive breast cancers with sentinel lymph node (SLN) surgery and/or axillary lymph node dissection (ALND). Completion ALND in the setting of one or two positive sentinel lymph nodes is at the discretion of the treating surgeon. Surgeons are encouraged to perform ALND for patients with three or more positive sentinel nodes or evidence of extra nodal extension in any of the positive sentinel nodes. The status of the axilla will be documented in the trial data collection.

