7.3 Pathology

Margin assessment of each lumpectomy specimen is required. For this study negative margin is defined as no tumor at ink. The size of the closest margin should be measured and reported for each lesion. The anterior and posterior margins are excluded from this restriction if the fascia and/or skin are taken.

When 2 or more lesions are excised en bloc, surgical pathology review is required to assess whether the lesions are separate foci of cancer separated by 2 cm or more of healthy breast tissue.

In consenting patients, tissue from each site of disease within the breast will be submitted for tissue banking and correlative science section. Tissue from axillary lymph nodes (sentinel lymph nodes and/or axillary lymph node dissection dependent on case) will also be collected for correlative science evaluation.

Patient may remain on study if, upon pathological assessment, two or three lesions identified on pre-operative imaging represent one contiguous lesion.

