16.2 Study Endpoints

The primary endpoint for this trial is the diagnosis of a local recurrence as a first event where a local recurrence is defined as histologic evidence of ductal carcinoma *in situ* or invasive breast cancer in the ipsilateral breast or chest wall.

The cumulative incidence of local recurrences will be estimated in the competing risk framework as described by Marubini and Valsecchi where regional recurrences, distant recurrences and death without a local recurrence will be considered competing risks and contralateral breast and non-breast second primary cancers will not be considered competing risk.

All eligible patients who have undergone breast conservation surgery with 2 or 3 sites of disease resected to negative margins (i.e., not converted to mastectomy or have not refused mastectomy for positive margins) will be included in the analysis of the primary endpoint.

Secondary clinical endpoints are:

- The conversion rate to mastectomy secondary to persistent positive margins; poor cosmesis within the first year of attempting breast conservation surgery (BCS); or inability to satisfy radiation dose constraints on the boost to the lumpectomy bed of each site of disease
- The type and severity of adverse effects of breast conserving surgery and radiation for women with multiple ipsilateral primary breast cancer (MIBC)
- The radiation-related side effects of whole breast radiation with a boost to 1 large or > 1 lumpectomy site
- The patient's perception of cosmesis.

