16.63 Analysis of Patients With Margins <2mm

A subset analysis will be done of patients with close margins (< 2 mm) who did not undergo re-excision.

The purpose is to see whether the inclusion of these patients inflated the local recurrence (LR) rate. In addition, the LR rate of patients with close margins (< 2 mm) who did not undergo re-excision will be estimated with point estimate and 95% confidence interval.

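### Goal 2.22 uses the term negative margins differently from Sections 7.2 and 7.3, and Section 16.63 does not estimate the close-margin comparison that the goal asks for

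*Combined protocol and SAP*

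**What the plan says.** Section 2.22 is a secondary goal. Its test group is women with margins under 2 mm who were not re-excised, and the question is whether they "have a higher local recurrence (LR) rate than patients for whom negative margins were achieved". The section is headed "2.22 Analysis of Patients Without Negative Margins".

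Section 7.3 gives the definition: "For this study negative margin is defined as no tumor at ink". Section 7.2 makes it a surgical requirement: "Each tumor must be resected to negative margins (no tumor at ink". The primary analysis set in Section 16.2 is limited to women with "2 or 3 sites of disease resected to negative margins".

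The matching analysis is Section 16.63: "A subset analysis will be done of patients with close margins (< 2 mm) who did not undergo re-excision". It continues: "The purpose is to see whether the inclusion of these patients inflated the local recurrence (LR) rate". The rate in the subset "will be estimated with point estimate and 95% confidence interval".

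Three further facts bear on the point. Section 7.3 has the closest margin measured for each lesion, and exempts anterior and posterior margins where skin or fascia was taken. Section 16.61 lists the factors for Gray's test, and margin width is not among them. The list of secondary endpoints in Section 16.2 does not include the close-margin comparison.

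**The concern.** There are two linked problems.

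The first is wording. Section 2.22 treats women with close margins as lacking negative margins, while Sections 7.2 and 7.3 count them as having negative margins as long as no tumor touches ink. A statistician who applies the protocol's own definition gets a comparator that includes the test group. One who follows the heading gets two separate groups. The plan does not say which is intended.

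The second is that the goal has no planned estimate on either reading. Section 16.63 names no comparator group, between-group difference, ratio or test. A rate for one group and a change in the overall rate are different quantities from the difference that 2.22 asks about.

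What is at stake is a secondary question: whether close but clear margins carry more local recurrence. As the text stands, the analyst must choose the comparator and the contrast when the data are already in hand.

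**Working it through.** **Inputs from the documents.** Section 16.3: 200 evaluable patients, with at most 8 first-event local recurrences for the upper 95% bound to fall below 8%. Section 16.51: the trial stops if more than 8 are seen. The documents give neither the close-margin share f nor an effect size.

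**The plan's own figure.** Exact two-sided 95% Poisson upper bound = χ²(0.975; 2(x+1)) / 2 / 200. For x = 8 it is 7.88%, and for x = 9 it is 8.54%. So 8 is the largest count that passes, and the stated figure reproduces. The rate at that count is 8/200 = 4.0%.

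**Which quantity each analysis gives.** Let p_c be the 5-year rate in close-margin women, p_w the rate in the rest, and f the close-margin share. The overall rate is p = f·p_c + (1 − f)·p_w. Then:

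- direct contrast, as in 2.22 with separate groups: p_c − p_w
- rise in the overall rate, as in 16.63: p − p_w = f·(p_c − p_w)
- close-margin women against all women with no tumor at ink, the literal reading of 2.22: p_c − p = (1 − f)·(p_c − p_w)

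**Numbers, under assumptions.** Overall rate fixed at 4% and risk ratio RR of 3 or 2, so p_w = 4% / (1 − f + f·RR) and p_c = RR·p_w. For f = 20% and RR = 3: p_w = 4% / 1.4 = 2.86%, p_c = 8.57%, difference 5.71 points, rise 4.00 − 2.86 = 1.14 points.

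| f | Difference, RR 3 (points) | Rise in overall rate, RR 3 | Difference, RR 2 | Rise, RR 2 |
|---|---|---|---|---|
| 10% | 6.67 | 0.67 | 3.64 | 0.36 |
| 20% | 5.71 | 1.14 | 3.33 | 0.67 |
| 30% | 5.00 | 1.50 | 3.08 | 0.92 |
| 40% | 4.44 | 1.78 | 2.86 | 1.14 |
| 50% | 4.00 | 2.00 | 2.67 | 1.33 |

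On the literal reading only, f = 20% and RR = 3 would give 8.57 − 4.00 = 4.57 points, which is 80% of 5.71.

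**Precision.** With f = 20% there are 40 close-margin women. Two recurrences give 5.0% (exact 95% CI 0.6% to 16.9%), and three give 7.5% (1.6% to 20.4%). Across f = 10% to 50%, the power of Fisher's exact test for the direct contrast (two-sided 0.05, N = 200, overall rate 4%) is 17% to 31% at RR 3 and 8% to 14% at RR 2.

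**The case against.** The strongest reply is that the heading of 2.22 shows the intent: close-margin women on one side and everyone else on the other. On that reading nothing overlaps. This stands as a statement of likely intent, but the text never defines the second group by width, and the term it uses has a different meaning in Sections 7.2 and 7.3.

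A second reply is that 16.63 already supplies the parts. The with/without look needs the rate in the remaining women, and subtracting it from the subset rate gives the difference. That is true of the point estimate. It leaves the difference without an interval, and the plan does not say that it will be reported. The rise in the overall rate answers its own stated question correctly and is not a biased estimate of the difference. The objection to it is only that it does not answer 2.22.

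A third reply is that about 8 events cannot support a useful contrast, so a subset rate with an interval is a reasonable choice. The power figures bear this out, and they rule out a confirmatory test. They do not argue against reporting the difference with its interval.

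Two stronger readings are tempting. A reader might infer that the planned result will be diluted towards no difference. That follows only if 2.22 is taken literally, and 16.63 plans no comparison of the part with the whole. A reader might also infer that the plan would lead to close margins being called safe to leave. The documents do not support this: 16.63 contains no test and no safety conclusion, and the interval it requires would be too wide for such a claim under the counts shown.

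**Conclusion.** The point holds as a mismatch between a secondary goal, the protocol's definition and the planned analysis. The term in 2.22 conflicts with 7.2 and 7.3, and no planned analysis reports the difference that 2.22 asks about. The quantity that 16.63 does plan shows a fraction f of that difference: one tenth at f = 10% and one half at f = 50%. The identity does not depend on the assumed rates. The point values rest on the assumed share and risk ratio and on an overall rate of 4%, the highest that the design accepts, and they treat every woman outside the close-margin group as one comparator.

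The importance is minor. The primary estimate and its 8% criterion do not change, and a correctly specified contrast will still be imprecise.

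**What to change.** In 2.22 and 16.63, define two non-overlapping groups by the closest evaluable margin across all of a patient's lesions: clear but under 2 mm and not re-excised, and 2 mm or more. State where two further cases belong: women who were re-excised and still have a clear margin under 2 mm, and anterior or posterior margins exempted in 7.3. Reword the heading and text of 2.22 so that the term agrees with 7.2 and 7.3.

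Report the difference in 5-year cumulative incidence of local recurrence, in the competing-risk framework already used in 16.61, with its 95% confidence interval. Label it descriptive and imprecise, because the design turns on about 8 events in 200. Keep the subset rate and the primary rate with and without these women as supplements.

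The cost is a few sentences in the plan, a little more analysis and a wide interval to explain. No new data are needed, and the surgical margin requirement is not touched.
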